## 7.2 Deviations from the Clinical Study Protocol

Deviations will be described in a single table by the numbers and percentages of patients in the Safety Population who were associated with at least 1 deviation and with at least 1 major deviation. Protocol deviations deemed “major” are defined as those that may significantly affect the completeness, accuracy, and/or reliability of the study data or that may significantly affect a patient's rights, safety, or well-being. The numbers and percentages of patients falling into each deviation category (listed below) will be summarized for major and minor deviations combined.

- Inclusion/exclusion criteria
- Informed consent issue
- Out of window visit
- Protocol required evaluation not completed
- Non-compliance with study drug administration
- Received excluded treatment
- Developed withdrawal criteria but not withdrawn
- Other

Patient-level data listings will be used to disclose the timing, category, and major/minor status of all deviations and, separately, just the deviations specifically associated with non-adherence to inclusion/exclusion criteria.

## 7.3 Demographic and Other Baseline Patient Characteristics

Demographic and other baseline characteristics of patients recorded during screening will include age, sex, childbearing potential (if female), pregnancy status (if female), ethnicity (Hispanic or Latino, not Hispanic or Latino, not reported, and unknown), race (American Indian or Alaska Native, Asian, Black or African American, Native Hawaiian or Other Pacific Islander, White, and not reported), blood type (O, A, B, and AB), and Rh factor (positive, negative). For patients in the Safety Population, a single table will be generated to summarize all patient characteristics, with age summarized as a continuous variable and all others summarized as categorical variables. Additionally, a single patient-level data listing will be provided to disclose all individually recorded baseline characteristics, except pregnancy status. All pregnancy test results (including baseline and post-baseline results) will instead be disclosed in a separate patient-level data listing, dedicated to the results of chemistry laboratory tests.

## 7.4 Prior and Concomitant Medications

The use of prior medications and concomitant medications will be summarized in separate tables as the numbers and percentages of patients in the Safety Population who used medication within each reported hierarchy of WHO Drug Anatomical-Therapeutic-Chemical (ATC) Levels 1, 2, and 3 and WHO Drug preferred name. Medications with partial start and/or stop dates, which cannot be definitively categorized as prior or concomitant, will be considered concomitant. The details of prior and concomitant medication use will be disclosed in a single patient-level data listing.

## 7.5 Concomitant Procedures

In addition to concomitant medications (described immediately above), patients may undergo procedures during the study for reasons of an adverse event, their medical history, a concomitant treatment (including medication and another procedure), or other indication. In tabular form, concomitant procedures will be described by the number and percentage of patients in the Safety Population who received at least 1 concomitant procedure and by the numbers and percentages of concomitant procedure recipients who fell into each category of reason for procedure. Data describing concomitant procedures will also be provided in a patient-level data listing.

## 7.6 Medical and Surgical History

Medical/surgical history, including all clinically-significant events, conditions, and previous surgeries, will be described in a patient-level data listing encompassing all patients from the Safety Population.

## 7.7 Neurological Examination

A neurological examination, comprising 18 elements of assessment (listed below), will be performed at screening. In a single patient-level data listing, the categorical results of each assessment (normal, abnormal, and not done) will be disclosed for individual patients in the Safety Population.

1. With eyes closed: Romberg Test
2. With eyes opened: tandem gait
3. Walk on tip toes
4. Walk on heels
5. With eyes closed: check for pronator drift
6. Finger-to-nose test
7. With eyes opened: play the piano
8. Rapid tapping or alternating movements
9. With eyes closed: eyeballs shut tightly
10. With eyes opened: observe pupillary reflex
11. Grin
12. Stick tongue out
13. Rapid tongue movements
14. Visual fields by confrontation
15. Eye movements
16. Reflexes
17. Babinski
18. Fundoscopy

## 7.8 Laboratory Archive Samples

A single patient-level data listing will be provided to disclose the details of the laboratory archive samples collected during screening, including date/time of collection and reason if not collected.

## 8 SAFETY ANALYSES

Several measures of safety will be examined in this study, with all safety summaries and analyses based on data collected from the Safety Population. Statistics describing these measures will be presented within tables and figures and derived for each patient cohort (dose level), as well as all patients combined (see **Appendix 2** for proposed data summaries). For all measures, data will also be disclosed in patient-level data listings.

### 8.1 Adverse Events

For AEs in this study, tabular summaries will provide the total numbers of events (and numbers and percentages of patients who experience events) by such event characteristics as the timing of the event (pre-treatment AE vs. TEAE), timing of TEAE (through Day-6 visit vs. after Day-6 visit through Day-30 visit), MedDRA SOC x PT classification, seriousness of the event, criteria satisfied for SAE classification (including death), severity grade, relationship with the underlying disease, relationship with the investigational product, and subsequent discontinuation of study participation (see also Section 3.2, Safety Assessments, for definitions). Within SOC x PT summaries, each patient will be counted only once per SOC x PT combination. TEAEs indicated by abnormal coagulation results, TEAEs classified as neurological, and treatment-related TEAEs specifically defining the study's suspension and stopping rules (i.e., thromboembolic events, stroke, acute lung injury, anaphylaxis, and death) will also be summarized.

Tabular summaries will incorporate data describing all AEs (both non-serious and serious) reported through the Day-6 visit (potentially through Day 10) and only SAEs reported following the Day-6 visit and through the Day-30 visit (potentially through Day 32). To disclose the details of all AEs/SAEs falling into these time-frames, multiple patient-level data listings will be generated, dedicated to solely AEs, solely SAEs, SAEs deemed treatment-related, SAEs deemed at least possibly treatment-related, AEs leading to study discontinuation, patient deaths, and AEs classified as neurologic, thromboembolic, stroke, acute lung injury, and anaphylaxis. A separate patient-level data listing will be used to disclose any non-serious AEs that are documented after the Day-6 visit and, thus, not included in the tabular summaries.

### 8.2 WHO Bleeding Severity Scores

Within multiple tables, the numbers and percentages of patients will be presented by highest WHO bleeding severity score (no bleeding/grade 0, grade 1, grade 2, grade 3, or grade 4), with "highest severity score" defined as the score associated with the most severe bleeding site (given documentation of multiple sites) for the nominal time-point of interest. This distribution of highest WHO bleeding severity scores not only will be presented by nominal time-point but also will be presented by post-baseline time-points relative to baseline time-point (to allow for assessment of shift) and by both bleeding site and time-point. Differences between patient cohorts (dose levels) in the proportion of the study population showing grade 2 or higher bleeding severity for the most severe bleeding site will be tested for statistical significance per time-point using Fisher's exact test, with results displayed in a single table. To facilitate visual examination of trends, 1 or more of the summaries described above may be presented within supplementary clustered bar charts or line chart overlays.

The numbers and percentages of patients will also be presented by grade-level change in WHO bleeding severity (-2, -1, 0, +1, +2, and +3) from baseline to post-baseline time-points for the patient's most severe bleeding site at baseline, by indication of increased bleeding severity from baseline to post-baseline time-points for the patient's most severe bleeding site at baseline, and by

indication of development of new bleeding sites from baseline to post-baseline time-points. Lastly, the details of all WHO bleeding assessments will be presented in a patient-level data listing. To facilitate, within this listing, visual examination of possible post-infusion changes in bleeding severity or number of bleeding sites as associated with protocol-defined windows for the timing of infusion relative to screening (i.e., within 24 hours [as stipulated in CSP v1.1] vs. within 4 days [as stipulated in CSP v2.0+]), the data listing will be sorted first by the screening assessment dates of patients and then, within individual patients, by assessment date.

Importantly, patients with multiple bleeding sites may show tied bleeding severity scores. For summaries in which patients' highest severity scores will be reported independently by visit or by visit and bleeding site (as described in the first paragraph of this section), tied scores will have no consequence and the highest score reported will simply represent multiple bleeding sites. However, for summaries in which each patient's most severe bleeding site is selected at baseline and tracked across subsequent time-points (as described in the paragraph immediately above), bleeding site selection will depend on continued comparison of severity scores across subsequent time-points until the tie in severity score is broken. For example, if a tie in severity score exists at baseline, the bleeding sites involved in the tie will be compared using scores recorded at the patient's next visit (i.e., 1-hour post-infusion) and the site of highest severity will be selected. If scores are still tied at 1 hour following infusion, then scores from the 6-hour post-infusion visit will be compared, and so forth.

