#### **Grade 4:**

- Any bleeding associated with severe hemodynamic instability (hypotension;  $>50$ mm/Hg fall or  $>50\%$  decrease in either systolic or diastolic blood pressure, with associated tachycardia (heart rate increase of  $> 20\%$  for 20 minutes) and requiring RBC transfusion over routine transfusion needs
- Fatal bleeding from any source
- Retinal bleeding with visual impairment (Visual impairment is defined as a field deficit, and patients with suspected visual impairment require an ophthalmologic consult for documentation)
- CNS symptoms with non-traumatic bloody lumbar puncture
- CNS bleeding on imaging study with or without dysfunction

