## 2.2 Study Endpoints

### 2.2.1 Primary Endpoints

Several primary endpoints will be quantified per patient cohort (i.e., by dose level), as well as overall (i.e., across all 3 dose levels):

- Overall frequency of (and number and percentage of patients who experience) TEAEs and TESAEs, including serious adverse drug reactions and treatment-related events specifically defining the study's suspension and stopping rules (i.e., thromboembolic events, acute lung injury, anaphylaxis, and death).
- Numbers and percentages of patients by highest WHO bleeding severity grade at baseline and post-baseline time-points, by highest severity grade at post-baseline time-points relative to baseline (allowing for assessment of shift), by both highest severity grade and bleeding site at baseline and post-baseline time-points, and by indication of a maximum severity grade  $\geq 2$  across bleeding sites at post-baseline time-points.
- Numbers and percentages of patients by grade-level change in WHO bleeding severity (e.g., -2, -1, 0, +1, +2, +3) from baseline to post-baseline time-points for the patient's most severe bleeding site at baseline, by indication of increased bleeding severity from baseline to post-baseline time-points for the patient's most severe bleeding site at baseline, and by indication of newly-developed bleeding sites from baseline to post-baseline time-points.
- Statistics describing (and/or graphics showing) central tendency and variability in coagulation, hematology, and serum chemistry measures across patients at baseline and post-baseline time-points, allowing for assessment of directional change in measures over time.
- Number and percentage of patients who shift from normal or clinically non-significant abnormal findings to clinically significant abnormal findings in coagulation, hematology, or serum chemistry measures between baseline and post-baseline time-points.
- Statistics describing central tendency and variability in vital signs, oxygen saturation (per pulse oximetry), and select 12-lead electrocardiogram (EKG) measures across patients at baseline and post-baseline time-points.
- Number and percentage of patients who shift in category of overall EKG interpretation from normal or clinically non-significant abnormal to clinically significant abnormal between baseline to post-baseline time-points.

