#### **6.4 Missing Values**

For all patients enrolled and all activities and assessments performed, every effort will be made to achieve complete data collection. Imputation is not planned for missing data, other than for missing date/time values. The missing component(s) of incomplete dates (e.g. start or stop dates of TEAEs, concomitant medication use, events/conditions in medical history) will be assumed to be the most conservative value possible. For example, if the start date is missing the day value, then the first day of the month will be imputed for study day computations. If the end date is missing the day value, then the last day of the month will be imputed. A similar approach will be used for missing month and year components. For complete dates but missing start or end times, values marking the beginning of the day (00:00:00AM) or end of the day (23:59:59PM), respectively, will be imputed. Importantly, date/time imputation will be used for computational purposes only; actual data values (as they appear in the database) will be presented in all patient-level data listings. Patients who withdraw consent for study participation or are lost to follow-up will be included in data summaries and analyses to the point of last contact.

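### A fatal bleed between the 24-hour and Day-6 visits has no defined place in the Day-6 WHO tables or Fisher test, although the scale grades it 4

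*SAP*

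**What the plan says.** - **Scale.** Protocol Appendix A lists under Grade 4: "Fatal bleeding from any source".
- **Tables.** SAP 8.2 classifies patients as "no bleeding/grade 0, grade 1, grade 2, grade 3, or grade 4", using the worst site "for the nominal time-point of interest". It adds shift tables, grade change at the worst baseline site, and new sites.
- **Test.** "Differences between patient cohorts (dose levels) in the proportion of the study population showing grade 2 or higher bleeding severity" are to be "tested for statistical significance per time-point using Fisher's exact test".
- **Status.** SAP 2.2.1 makes these summaries primary endpoints, including patients "by indication of a maximum severity grade" of 2 or more. That maximum runs across bleeding sites, not across time.
- **Schedule.** Protocol 1.9.3 and Table 4 place post-infusion WHO assessments at 1, 6 and 24 hours and at Day 6. SAP Table 3 gives the 24-hour visit a window of 3 hours either side and lets the Day-6 visit fall on Days 6 to 10.
- **Missing data.** SAP 6.4 says: "Imputation is not planned for missing data, other than for missing date/time values". Patients who withdraw or are "lost to follow-up will be included in data summaries and analyses to the point of last contact". Death is not named.
- **Out-of-window data.** SAP 6.2 allows unscheduled assessments to be left out of by-visit summaries or shown between the scheduled visits.
- **Population.** SAP 8 bases safety summaries on the Safety Population (all infused). It does not say whether a patient without a score stays in the denominator at that time-point.

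**The concern.** The worst outcome on the bleeding scale is death from bleeding, and the bleeding tables have no rule for receiving it. The exposed interval runs from about 27 hours after infusion (the end of the 24-hour window) to the Day-6 visit. A patient who dies of bleeding on Day 3, for example, produces no Day-6 score.

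Two things are at stake. The Day-6 grade distribution and shift table, which the SAP treats as primary safety results, would show less severe bleeding than occurred. The Day-6 comparison between dose levels would also be affected, so a dose with more fatal bleeds could look no worse than the others.

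Deaths are foreseen in this population. SAP 6.6 defines subgroups by survival to Day 30, but SAP 8.3 uses them only for white-cell tables. SAP 8.2 gives a detailed rule for tied scores and none for absent ones.

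**Working it through.** The documents give no bleeding, death or dropout rate and no power calculation (Protocol 1.13 and SAP 4 say the sample size has no statistical basis), so there is no figure of the plan's own to reproduce. All counts below are assumptions, apart from the cohort size of 8.

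**Step 1: direction for one fatal bleed.** Let n be the number infused and a the number of survivors at Grade 2 or higher on Day 6, with one death from bleeding before Day 6.
- Death coded Grade 4: (a + 1)/n.
- Assessed-only denominator: a/(n − 1). Shortfall = (a + 1)/n − a/(n − 1) = (n − 1 − a)/[n(n − 1)]. Since a cannot exceed n − 1, this is never negative.
- All-infused denominator, death not an event: a/n. Shortfall = 1/n.

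With n = 8, the all-infused shortfall is 1/8 = 12.5 points. The assessed-only shortfall is 7/56 = 12.5 points when a = 0 and 5/56 = 8.9 points when a = 2. Hence up to 12.5 points per fatal bleed.

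**Step 2: several deaths.** Cohort of 8 infused, k fatal bleeds before Day 6, 2 survivors at Grade 2 or higher:

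| k | Assessed only | All infused, death not an event | Death coded Grade 4 | Shortfall (points): assessed only / all infused |
|---|---|---|---|---|
| 1 | 2/7 = 28.6% | 2/8 = 25.0% | 3/8 = 37.5% | 8.9 / 12.5 |
| 2 | 2/6 = 33.3% | 2/8 = 25.0% | 4/8 = 50.0% | 16.7 / 25.0 |
| 3 | 2/5 = 40.0% | 2/8 = 25.0% | 5/8 = 62.5% | 22.5 / 37.5 |

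The Grade 4 share arising from these deaths reads 0 instead of 12.5%, 25.0% and 37.5%.

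SAP 4 targets 8 evaluable patients per dose, so more than 8 may be infused. With 10 infused and one fatal bleed, the comparison is 2/9 = 22.2% or 2/10 = 20.0% against 3/10 = 30.0%.

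**Step 3: Fisher's exact test across three cohorts** (two-sided, deaths in the third cohort only):

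| Deaths | Assessed only | p | Deaths coded Grade 4 | p |
|---|---|---|---|---|
| 2 | 1/8, 1/8, 1/6 | 1.00 | 1/8, 1/8, 3/8 | 0.56 |
| 3 | 2/8, 2/8, 2/5 | 1.00 | 2/8, 2/8, 5/8 | 0.36 |
| 4 | 1/8, 1/8, 1/4 | 1.00 | 1/8, 1/8, 5/8 | 0.062 |
| 4 | 0/8, 0/8, 0/4 | 1.00 | 0/8, 0/8, 4/8 | 0.020 |

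Of these four scenarios, only the last crosses 0.05. The descriptive percentages move in all of them.

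**Step 4: other missing scores.** Suppose 2 of 8 leave while at Grade 0 or 1, and 3 of the remaining 6 are at Grade 2 or higher. Assessed-only gives 3/6 = 50.0% against a true 3/8 = 37.5%, so here the table overstates bleeding. The direction found in Step 1 does not extend to withdrawals.

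**The case against.** The strongest reply is that no death is lost. SAP 8.1 summarises AEs by severity grade and by SAE criterion, including death. Table 14.3.2.8 is devoted to deaths, Listings 16.2.5.2 and 16.2.5.6 show them, and the DMC monitors them. AEs and SAEs are the protocol's primary endpoint, while Protocol 1.9.9 makes bleeding grade secondary. This stands. A reader might infer that fatal bleeding is never counted, and the documents do not support that. What is missing is its coding into the WHO outputs.

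A reader might also infer that Grade 4 cannot appear in the WHO tables. It can: the category exists, a Grade 4 recorded at a scheduled visit is tabulated, and an unscheduled one may be displayed. But display between visits is optional and, as I read SAP 6.2, would not fill the Day-6 row or enter the Day-6 test.

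Nor do the documents say that patients who die drop out of the denominator. SAP 6.4 speaks of withdrawal and loss to follow-up only, and the denominator is undefined. For a fatal bleed this ambiguity does not help, because Step 1 shows a shortfall under both readings whenever at least one surviving patient is below Grade 2.

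Finally, this is a small, largely descriptive Phase 1 study, the counts above are assumed, and the test result often would not change. That limits the size of the point. It does not remove the inconsistency between the scale and the tables.

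**Conclusion.** The point holds in a limited form. Under the stated rules, a death from bleeding between the 24-hour and Day-6 visits has no route into the Day-6 WHO distribution, shift table or between-cohort test, although the protocol's own scale makes it Grade 4. The understatement is up to 12.5 percentage points per fatal bleed in a cohort of 8. This assumes that 8 are infused and that such a death occurs; the documents give no rate for it.

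It would go too far to conclude that Day-6 bleeding will always look milder than it was. The direction is fixed only for fatal bleeding, and patients missing for other reasons can shift the percentages either way. It would also go too far to expect the Fisher result to change, which in these illustrations needed four fatal bleeds in one cohort and no other Grade 2 or higher patients. The main harm is to the descriptive tables of an endpoint that the SAP calls primary, and it should be corrected before database lock.

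**What to change.** In SAP 8.2:

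1. Code a death caused by bleeding as Grade 4 at the first scheduled WHO time-point after death and at any later one, in Tables 14.3.3.1, 14.3.3.3 and 14.3.3.4.
2. State that the denominator at every time-point is all infused patients. Add separate rows for patients who died of causes other than bleeding and for patients not assessed (withdrawn or missing). Give the assessed-only result alongside, including for the Fisher test.
3. In the site-tracking tables (14.3.3.5 and 14.3.3.6), count the death as an increase only if the fatal bleed was at the tracked baseline site. If it was at a new site, count it in Table 14.3.3.7.
4. Keep deaths to which bleeding only contributed for a sensitivity analysis, since Appendix A refers to fatal bleeding and does not mention contribution.

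The cost is a few lines of SAP text, two table rows and a short derivation from death and AE data already collected. Reported bleeding rates may be slightly less favourable.

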### 1.9.2 Methodology

This is a Phase 1, multicenter, open-label, dose-escalation study in hospitalized, bleeding, and thrombocytopenic patients. Patients with modified WHO Grade 1 (see note following Table 1. Cohort Assignment) or Grade 2 bleeding due to hematology/oncology diseases or bone marrow aplasia secondary to cancer chemo/radiotherapy will be enrolled on study and treated with allogeneic Thrombosomes (See

Appendix A- Modified WHO Bleeding Score). Patients with WHO Grade 0, 3, or 4 bleeding do not meet eligibility criteria for enrollment. The protocol will require three cohorts of patients consisting of 8 patients in each cohort for a total of 24 patients (See Table 1. Cohort Assignment).

Table 1. Cohort Assignment				
Cohort	1	2	3	Total
	n	n	n	n
WHO Grade 1*or 2	8	8	8	24

Note: \*Only a subset of patients with Grade 1 bleeding who have either epistaxis, hematuria, oral petechiae, oropharyngeal bleeding, or bleeding at invasive or other wound sites.

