### **1.16 Data Analysis**

Separate data summaries will be prepared for each cohort:

- Demographic and medical history data will be summarized. For quantitative variables, summaries will include the sample size, mean, median, standard deviation, minimum, and maximum. For qualitative variables summaries include the number and percent of patients for each outcome.
- Exploratory analyses will include the observed response and the change from baseline to each of the post-infusion time points for each of the laboratory tests (hematology, coagulation, platelet and chemistry). Additionally, summaries of the number and percent of patients with both a change of  $>5\%$  from baseline and whose results are outside of reference ranges will be displayed. For quantitative variables summaries of the observed response and the change from baseline to each of the post-baseline time points will include the sample size, mean, median, standard deviation, minimum, and maximum. Additionally, for the change from baseline summaries, the statistical significance will be determined using either a t-test or the Wilcoxon Signed Rank test, as appropriate. Summaries for qualitative variables will include the number and percent of patients for each outcome.
- Incidence of AEs and SAEs per patient and by body system will be summarized showing the number and percent of patients for each outcome. Summaries will also be prepared by severity and relationship to treatment.
- Summaries of vital signs and clinical data including WHO bleeding scores will include the observed response and the change from baseline to each of the post-infusion time points for each of the variables. For quantitative variables summaries of the observed response and the change from baseline to each of the post-baseline time points will include the sample size, mean, median, standard deviation, minimum, and maximum. Additionally, for the change from baseline summaries, the statistical significance will be determined using either a t-test or the Wilcoxon Signed Rank test, as appropriate. Summaries for qualitative variables will include the number and percent of patients for each outcome.

A statistical analysis plan will be developed as part of the data analysis plan.

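### The SAP's only test on WHO bleeding cuts the grade at 2 or higher, so resolution of Grade 1 bleeding cannot register in it; add an exploratory exact rank test on the full grade

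*SAP*

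**What the plan says.** **Entry.** Protocol 1.9.2 admits Grade 2 bleeding and a subset of Grade 1 bleeding: "Patients with WHO Grade 0, 3, or 4 bleeding do not meet eligibility criteria for enrollment".

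**Objective.** Protocol 1.8.2 makes the effect of increasing doses on the WHO bleeding score a secondary objective.

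**Test in the SAP.** SAP 8.2 compares cohorts "in the proportion of the study population showing grade 2 or higher bleeding severity" at the worst bleeding site. These differences "will be tested for statistical significance per time-point using Fisher's exact test, with results displayed in a single table" (Table 14.3.3.4). The cut comes from SAP 2.2.1, which counts patients "by indication of a maximum severity grade" of 2 or more among the primary endpoints.

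**Description in the SAP.** SAP 8.2 also tabulates the whole scale ("no bleeding/grade 0, grade 1, grade 2, grade 3, or grade 4"), shifts from baseline, new sites, and "grade-level change in WHO bleeding severity (-2, -1, 0, +1, +2, and +3) from baseline to post-baseline time-points". That change follows the site graded worst before infusion. None of these summaries carries a test.

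**Protocol analysis text.** Protocol 1.16 says: "Summaries of vital signs and clinical data including WHO bleeding scores will include the observed response and the change from baseline". It adds that "for the change from baseline summaries, the statistical significance will be determined using either a t-test or the Wilcoxon Signed Rank test". SAP 8.3 keeps a signed-rank test for laboratory measures. SAP 8.2 has none for WHO scores, and SAP Section 11 does not mention this.

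**The concern.** The WHO grade is an ordered five-level score, recorded for every patient at every bleeding assessment, and the SAP's one test reduces it to two levels. With entry limited to Grades 1 and 2, the cut falls between the two entry grades. A Grade 1 entrant can then affect the result only by getting worse. A Grade 2 entrant can improve only by crossing to below 2, and how far below makes no difference.

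This will be the only p-value the SAP produces on WHO bleeding. If many patients enter at Grade 1, a non-significant result says little about dose and bleeding, yet it could be read as showing no effect. With 8 patients per cohort and no power basis for that number (SAP Section 4), there is little information to spare.

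**Working it through.** The documents state no power or effect size for WHO bleeding, so there is no figure of theirs to reproduce.

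**Inputs from the documents.** Three cohorts of 8 (SAP Section 4); two-sided 0.05 (SAP 6.8); no multiplicity adjustment (SAP 6.7); entry at Grade 1 or 2.

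**Assumptions.** Share g of patients entering at Grade 2: 25%, 50% or 75%. Chance i of a one-grade improvement in cohorts 1/2/3: 0.10/0.45/0.80, the same for both entry grades. Chance w of a one-grade worsening: 0.05.

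**Step 1: what the cut can see.** After infusion,

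P(grade ≥2) = (1 − g) × w + g × (1 − i).

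The improvement rate of Grade 1 entrants does not appear in this expression; only their worsening does. The result would also be unchanged if the Grade 2 entrants who improve fell to 0 instead of 1.

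**Step 2: proportions entering Fisher's test.** For g = 0.50:

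- Cohort 1: 0.5 × 0.05 + 0.5 × 0.90 = 0.475
- Cohort 2: 0.5 × 0.05 + 0.5 × 0.55 = 0.300
- Cohort 3: 0.5 × 0.05 + 0.5 × 0.20 = 0.125

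The same formula gives 0.2625/0.175/0.0875 for g = 0.25 and 0.6875/0.425/0.1625 for g = 0.75.

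**Step 3: power.** Fisher's test (2×3) was evaluated by exact enumeration of three Binomial(8, p) counts. The rank tests are permutation Kruskal-Wallis tests, evaluated by simulation; repeat runs differed by up to about 4 points.

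| Grade 2 at entry | Fisher, grade ≥2 | Rank test, grade 0–4 | Rank test, change in grade |
|---|---|---|---|
| 25% | 4% | 47% | 67% |
| 50% | 16% | 37% | 64% |
| 75% | 34% | 45% | 67% |

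**Step 4: where the gain disappears or grows.** These runs use other assumed improvement rates, with the full grade as comparator.

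- All enter at Grade 2, 10/40/70%: Fisher 50.4%, rank test 50.0%. Over the three sets of rates tried (10/30/50, 10/40/70 and 5/50/90%), the difference was −5 to 0 points.
- Only Grade 2 entrants respond to dose, half enter at Grade 1, 10/40/70%: 11.2% against 13.7%. Over the four cases tried, −1 to +6 points.
- All enter at Grade 1, 10/40/70%: 0.1% against 50.2%.

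**Step 5: which change variable.** The change score in SAP 8.2 follows one site per patient. When sites tie at baseline, the one that scores higher after infusion is chosen. That is not the change in the patient's highest grade, and the two differ when a new site appears. The table in Step 3 uses one grade per patient, so it corresponds to the highest grade.

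**The case against.** **The cut has a purpose.** SAP 2.1.1 treats worsening bleeding as a safety indicator, the ≥2 cut is among the primary endpoints, and the test sits in Section 8, the safety analyses. A move from 1 to 2 does register. This stands, so the comparison should be kept. It does not meet the protocol's objective on the WHO score, and it also misses worsening from 2 to 3.

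**Improvement is reported.** A reader might infer that the analysis hides resolution of Grade 1 bleeding. It does not: the distribution, shift and change tables show it. The gap is in the test alone.

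**The power loss is conditional.** A reader might take one range of power loss as a property of the plan. The documents give no entry mix or effect size, and Step 4 shows that the loss can vanish or slightly reverse. Also, Appendix A grades oropharyngeal bleeding, epistaxis and invasive-site oozing over the previous 24 hours. At 1 and 6 hours that period still covers pre-infusion bleeding, so improvement as high as 80% is doubtful at those two of the four post-baseline assessments, on any scale.

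**Protocol 1.16 is unclear.** A reader might infer that a promised WHO test was silently removed. The significance test in 1.16 follows the sentence on quantitative variables, while qualitative variables get counts and percentages. The section does not say which type the WHO grade is. Section 11 claims only to list the most significant changes, and it does disclose the reworded objective and endpoints. What stands is a need to clarify.

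**Entry mix may differ by cohort.** Cohorts are sequential and not randomised. Grade 2 entrants have more room to fall, so a change score can differ between cohorts for that reason alone. This stands and shapes the fix. By the formula in Step 1, the Fisher proportions depend on entry mix too.

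**Conclusion.** The point holds in a limited form. The SAP's one WHO test cannot register a fall from 1 to 0 and cannot separate 2-to-0 from 2-to-1. This follows from the entry criteria and the cut and needs no assumption.

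The size does rest on assumptions. With equal one-grade improvement of 0.10/0.45/0.80 in both entry grades and 25–75% Grade 2 at entry, Fisher's power is about 4–34%, against about 37–47% on the full grade and about 65% on change in grade. The gain is near zero if all enter at Grade 2 or only Grade 2 entrants respond. It is larger if most enter at Grade 1. On the full grade a non-significant result stays more likely than not in these scenarios, so the added test is exploratory and would not turn this into a powered comparison.

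The documents do not support calling the cut an error or removing it. They support adding an ordinal test beside it.

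**What to change.** 1. In SAP 8.2 and Table 14.3.3.4, add an exact (permutation) rank test across cohorts at each post-baseline time-point on the highest WHO grade (0–4). Either permute within baseline-grade strata or test the change in highest grade, derived for this purpose and not taken from the single-site change in SAP 8.2. Stratifying deals directly with unequal entry mix. Label the test exploratory.
2. Keep the grade ≥2 Fisher comparison and describe it as the safety analysis of worsening.
3. State whether the change-from-baseline test in protocol 1.16 applies to WHO scores. If it does, either carry it into the SAP as uncontrolled and exploratory, or list its removal in Section 11.
4. If any power figure is quoted for these tests, give its assumptions with it.

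The cost is SAP wording, one derived variable if the change option is chosen, and one more statistic in an existing table. No new data are needed. The downside is one more unadjusted exploratory p-value per time-point, and a rank result is less easy to read than a percentage.
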